Evaluation Goal:

To evaluate the safety and acceptability of the ShangRing device for nonsurgical circumcision in routine clinical settings, as a part of a comprehensive HIV prevention program for males in VMMC programs.

Evaluation Endpoints:

Primary Endpoint: the proportion of males experiencing mild, moderate and severe adverse events (AEs) associated with ShangRing circumcision procedures, including both intra- and post-operative events, and all device-related malfunctions (e.g., early spontaneous detachment).

Secondary Endpoints:

- Training needed for proficiency using the ShangRing device, including number of procedures to become fully proficient at applying and removing the ShangRing device.
- Client and provider acceptability, client satisfaction, and duration of procedure.
- The percentage of clients clinically healed 49-52 days post-placement of the ShangRing device, and the time at which point all clients are clinically healed.

Evaluation Design

Training Phase: this phase will be used to evaluate the training requirements for implementation by mid-level providers, to preliminarily assess acceptability to providers, and to monitor logistical needs. Each clinician will perform no fewer than 10 ShangRing device placements, and 5 ShangRing removals before start of the next phase (implementation pilot).

Implementation Pilot: following the training period, 575 male clients will be recruited to undergo circumcision with the ShangRing device in the context of routine service delivery.

Data will be collected at up to at least 5 points in time: at enrollment and device placement (day 0), at device removal (day 7), during a follow-up phone call (day 10), in-depth qualitative interviews for 50 purposefully selected clients (day 28), at an in-person follow-up visit to assess wound healing (day 49), and at subsequent weekly visits to assess healing for those not completely healed at day 49.

Upon completion of the implementation pilot, the data will be analyzed and used to assist with policy decisions and recommendations on ShangRing use in adult male circumcision programs.

Section C: Protocol

Introduction

Voluntary Male Medical Circumcision (VMMC), VMMC Devices and ShangRing

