To evaluate the safety and acceptability of the ShangRing for device-based circumcision in routine clinical settings, as a part of a comprehensive HIV prevention program for males aged 13 and older in Tanzania.

Evaluation Objectives

The specific objectives of the proposed implementation pilot is to:

- Describe/assess the safety of the ShangRing device by the occurrence of clinical adverse events (calculated as a rate), when circumcision is performed by trained mid-level providers;
- Ascertain capacity and required clinical capabilities of clinical staff of various cadres to carry out ShangRing procedures;
- Describe/assess male client and provider acceptability of the ShangRing device and process (e.g. need to return to the clinic for device removal, tolerance for leaving device in situ);
- Assess the percentage of clients clinically healed 6 weeks (42 days) following the removal of the device;
- Determine the time at which point all clients are physically healed following the removal of the device.

Primary Endpoint

The primary endpoint related to the goal and objectives of the evaluation is to:

- Measure the incidence of mild, moderate and severe AEs associated with ShangRing procedures including both procedure and post-procedure events, and all device-related malfunctions such as early spontaneous displacement. The primary endpoint will be assessed at device placement, at device removal, 3-days post removal, at the day 49 post-placement healing assessment, and at any unscheduled visit in that time frame. Adverse events will be measured and described in the following ways:
 - Total numbers and types of known AEs occurring among clients, including all severities of AEs (mild, moderate, severe) and serious AEs (see below), including detailed information about all instances of device displacement/detachment/self-removal/malfunction, need for medical attention or intervention, and final outcomes in those experiencing AEs.
 - Total number of clients with known AEs (may be different from above if clients experience multiple AEs), including all severities of AEs and serious AEs.

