Phase 2: Implementation Cohort Evaluation	455-495 (Depending upon # performed during training phase)	
Safety Component
 
Primary endpoints:
 
 - Adverse events and device-related incidents 
Secondary endpoints:
 
 - Safety of procedure/removal - Provider perception of technical difficulty and complications during procedure and removal process 
Provider Acceptability Component:
 
 - Provider acceptability - Practicality of device use - Procedure and removal times 
Client Acceptability Component:
 
 - Client satisfaction - Cosmetic results - Comfort: 
 - During procedure to place device - During (nocturnal) erections - During removal 
Healing Component
 
 - Percentage of men clinically healed 49-52 days post placement (42 days post-removal) - Time at which point all men are clinically healed 	
Standardized forms to collect data on adverse events and device-related adverse events
 
Client records
 
Brief surveys to collect data on reasons to decline participation in the evaluation as indirect measure of acceptability
 
Brief surveys to collect data on client experience with the ShangRing as an indirect measure of acceptability
 
Qualitative interview with providers
 
Qualitative interviews with 50 male clients
 
Qualitative interview with providers
 
Brief surveys to collect data on reasons to decline participation in the evaluation as indirect measure of acceptability
 
Client records – including those recording application and removal times
 
Client records indicating healing per VMMC healing definition as completed by providers during day 49 healing assessment visit and subsequent weekly healing visits for those not healed at day 49
 
Photographs of the client's genital area, to be taken post-device removal (day 7), and at the day 49 healing assessment visit and at subsequent weekly healing visits

Evaluation Procedures and Logistics

Evaluation Offices

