AE and other incidents that occur as a result of the ShangRing device will be recorded as part of this evaluation. All events and incidents – including mild, moderate and severe AE, expected side effects such as common post-operative findings, occurrences resulting from clients' failure to follow instructions, and device malfunctions – will be documented on the appropriate visit section and device-related events form of the CRF. Events classified according to the definitions provided as mild, moderate and severe based on the PEPFAR AE definitions below should also be recorded on the adverse events form of the CRF. The adverse events form will include a description of the onset, duration, relationship to the procedure, severity, seriousness, and final outcome of the AE. For additional information on severity criteria by type of AE see Appendix XV.

For the purposes of this evaluation AEs that are related to the evaluation device will be graded using the following definitions as guides:

- Definitely related: direct association with the procedure, i.e., follows a reasonable temporal sequence and is a recognized AE of the procedure. Note that this does not imply any error on the part of the provider or client, only that the event would not have happened if the procedure had not been performed.
- Likely/possibly related: more likely explained by the procedure, i.e., follows a reasonable temporal sequence from the procedure and is a plausible AE of the procedure, but could have another cause.
- Likely unrelated: more likely explained by another cause.
- Definitely unrelated: clearly explained by another cause.

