A physician will evaluate each AE for severity, seriousness, and relationship to the MC procedure, per the categories and criteria delineated in the *AE Action Guide for Voluntary Medical Male Circumcision by Surgery or Device, 2nd Edition* (see Appendix XV for table of AEs and severity). To ensure objectivity, the evaluating physician will be brought in from a site other than where the circumcision was performed. Any evaluating physician should be trained in male circumcision, and have experience evaluating adverse events. Methods to assess the severity, seriousness and relatedness of the AE are detailed in the evaluation SOP manual. Evaluation physicians will be trained to make these assessments in a manner as standardized as possible. The site coordinator will verify that this information will be captured during every evaluation subject visit. AEs will be managed medically as appropriate, and will be followed until resolution or until a clinically stable endpoint is achieved.

The incidence and severity of all AEs related to the circumcision procedure will be documented and collected on the appropriate visit section and device-related events form of the CRF. This form will include a description of the onset, duration, relationship to the procedure, severity, seriousness, and final outcome of the AE. Severe and serious AEs, as well as AEs related to client self-removal of the ShangRing, will also be documented on the ShangRing Device Related Adverse Events form (see Appendix XIV), which must be completed for all AEs that result in hospitalization and all AEs classified as severe per the AE classification guidelines, as well as for those whose severity cannot be classified. The evaluation will compile and analyze mild, moderate and severe AE to determine the AE rate. All other device-related events, including expected side effects and occurrences resulting from clients' failure to follow instructions, will be compiled and summarized to inform program policy related to ShangRing use.

For the purposes of this evaluation, **all** severe AEs must be reported to the CDC **within 24 hours of notification**. Standard reporting procedures for all **notifiable** AEs must be followed per PEPFAR and national guidelines.

ShangRing and Tetanus

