Baseline demographics and client characteristics will be presented in tabular format using descriptive statistics. Binary data such as adverse events will be presented as counts and percentages and the upper limit of the estimate of the AE rate (percent of clients with one or more AE) will be based on a two-sided 95% confidence interval. Adverse event rates will be compared descriptively with the reported rates of similar treatments reported in Tanzania and elsewhere, including: comparison against AE rates found in other studies of ShangRing, comparison against AE rates found in studies of other circumcision devices, and comparison against reported rates of AEs in studies of surgical circumcision. No formal hypothesis tests will be done comparing AE rates in this evaluation to other AE rates.

Adverse event rates will be presented by seriousness, severity, relation to device and outcome by site and by cadre. Continuous data will be represented by a mean, standard deviation, median, minimum and maximum together with 95% confidence intervals for the means. The number and percent of subjects who fail to complete the evaluation will be assessed. Time to withdrawal may also be assessed. The procedure time will be calculated. The first 15 procedures performed by each provider will be compared to the last 15 procedures by that provider with respect to procedure time, to evaluate whether procedure time is shortened with experience. All of the first and last 15 procedures evaluated will take place during the main implementation pilot phase. If a provider does not perform 30 total procedures following the training phase, then the first half of the total number of procedures performed will be compared against the last half. Adverse event rates from the training and post-training phases will also be reported, as well as an overall AE rate. Procedure times during the provider training phase will be tracked, but not used for comparisons. The differences in mean procedure times will be compared with a t-test or a non-parametric equivalent.

Standard statistical software packages R, Stata or SAS will be used for the analysis. No corrections for missing values will be imputed. The data will be analyzed and presented “as-is”.

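### The primary safety rate has no single numerator: device malfunctions belong to the endpoint, drop out of the AE rate by implication, and have no consistent place on the forms

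*Protocol*

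**What the plan says.** **Endpoint.** Under Evaluation Endpoints (Executive Summary) the primary endpoint is the proportion of males with mild, moderate and severe AEs, and it also takes in "all device-related malfunctions (e.g., early spontaneous detachment". The Primary Endpoint section repeats this: "and all device-related malfunctions such as early spontaneous displacement". Table 2 gives the Phase 2 primary endpoint as "Adverse events and device-related incidents".

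**Rate.** The section on AE and device-related incident documentation says: "The evaluation will compile and analyze mild, moderate and severe AE to determine the AE rate". The next sentence begins "All other device-related events, including expected side effects and occurrences resulting from" clients not following instructions, and has these summarised to inform programme policy. Earlier, the same section lists what is to be documented: graded AEs, expected side effects, and then events from clients' "failure to follow instructions, and device malfunctions".

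**Confidence limit.** The Analysis Overview attaches the two-sided 95% interval to "the upper limit of the estimate of the AE rate (percent of clients with one or more AE".

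**Forms.**
- The documentation section says events graded "mild, moderate and severe based on the PEPFAR AE definitions below should also be recorded on the adverse events form of the CRF".
- Appendix XVIII limits that AE form to moderate or severe events. Staff are told to leave it empty otherwise, and its severity field has only those two boxes.
- The placement form (Appendix IX) lets staff mark an AE's severity as not classifiable and names device malfunction as a reason. Appendices IX and XII both send unclassifiable events to the AE form.

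**The concern.** The AE rate and its upper limit are the main safety result passed to the ministry. A client whose only event is an ungraded malfunction is in the primary endpoint, is not in the rate as the documentation section builds it, and is in the Analysis Overview's rate only if someone recorded the event as an AE. With about a dozen affected clients expected, a few such cases change the result visibly.

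Reporting by severity does not settle this, because an event without a grade falls in no severity stratum. Nor can the forms settle it: some events are sent to a page with no box for them.

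**Working it through.** **1. The plan's own precision figure.** Inputs from the sample-size section: AE rate 2%, half-width 1.5 points, 95% confidence.

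n = 1.96² × 0.02 × 0.98 / 0.015² = 334.6, rounded up to 335. This agrees with the protocol. At n = 575 the half-width is 1.96 × √(0.02 × 0.98 / 575) = 1.14 points.

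**2. One event followed through the text.** Take a client whose ring detaches early, with no other finding.

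| Place | Counted? |
|---|---|
| Evaluation Endpoints | Yes; early detachment is the example given |
| Primary Endpoint | Yes, as a device malfunction |
| Table 2, Phase 2 | Yes, as a device-related incident |
| Documentation section, rate sentence | Only if graded mild, moderate or severe |
| Analysis Overview | Only if recorded as an AE |

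Can the event be graded? Appendix XIX has rows for displacement (which covers self-removal) but none for detachment or other malfunctions. The device events form in Appendix XVIII lists displacement and detachment as separate event types. Displacement and self-removal are graded moderate or severe, so they count on any reading. The dispute is confined to detachment and other malfunctions that receive no grade.

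**3. The forms side by side.**

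| Event | Sent to the AE form by | What the AE form allows |
|---|---|---|
| Mild AE | Documentation section | Nothing to be entered |
| Unclassifiable event | Appendices IX and XII | No box; only Moderate and Severe |

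The device events form has a Mild box, so mild AEs are recorded there. Its severity field also lacks an unclassifiable option. It takes AEs, expected side effects and malfunctions together, with no field that states which of the three an entry is.

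**4. Size.** The protocol gives no malfunction rate, so the rates below are assumptions. They are taken to fall in clients with no other AE. The base is 2% of 575 = 11.5, taken as 12 clients. Limits are exact (Clopper-Pearson) 95%.

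| Ungraded malfunctions assumed | Added clients | Numerator | Rate | Upper limit |
|---|---|---|---|---|
| none | 0 | 12 | 2.1% | 3.6% |
| 0.5% (2.9) | 3 | 15 | 2.6% | 4.3% |
| 1% (5.75) | 6 | 18 | 3.1% | 4.9% |
| 2% (11.5) | 12 | 24 | 4.2% | 6.1% |

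At the assumed 1% the rate moves by 6/575 = 1.04 points, close to the 1.14-point half-width at 575. At 2% it moves by 2.1 points, which is more than that half-width.

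**The case against.** The documentation section never says that malfunctions are excluded. Its sentence on other events names expected side effects and non-adherence but omits malfunctions, although the earlier list has all three. It also treats events of unclassifiable severity as AEs, since it requires a report for them. The placement form offers the unclassifiable code only after staff have answered that an AE occurred, so an event coded that way meets the Analysis Overview's test. And the Primary Endpoint section calls for detailed information on every detachment and malfunction, so none need go unreported.

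All of this stands. It means that exclusion is an inference, and that the Analysis Overview can be read the inclusive way. It does not remove the conflict: the one sentence that says how the rate is determined names three grades, and an ungraded event has none of them. Full description of malfunctions does not say whether they enter the rate that carries the interval.

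A reader might also infer that mild AEs are lost from the rate. The documents do not support that. The endpoint and the rate sentence both include mild AEs, and the documentation section has the incidence and severity of all AEs collected on the visit section and the device events form. The clash concerns a second form.

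A reader might further infer that the sample size is wrong. It is not: 335 is correct, and 575 exceeds it. The protocol does not say which definition its 2% uses, and it describes a precision calculation as power. Those are wording points and do not carry this finding.

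**Conclusion.** The concern holds in a limited form. The protocol uses more than one numerator for its primary safety rate, and the documentation section and the Analysis Overview can give different rates from the same data. Separately, its text and forms give staff incompatible instructions for mild and unclassifiable events.

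It would go too far to say that the protocol expressly removes malfunctions from the rate. Their exclusion is implied by the three-grade rule, the separate listing, the placement form's code and the missing rows in Appendix XIX.

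The effect is 0.5 to 2.1 points on a base of 2.1%, with the upper limit rising from 3.6% to between 4.3% and 6.1%. This rests on the assumed malfunction rates of 0.5% to 2%, on no overlap with other AEs, and on all 575 clients in the denominator. If every malfunction is graded, or occurs only in clients who have another AE, the rate does not change. The point should be fixed because it concerns the numerator of the main safety result and costs little to put right.

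**What to change.** 1. In the documentation section and the Analysis Overview, state the numerator that the endpoint sections point to: a client with at least one mild, moderate or severe AE, or at least one device malfunction, including events whose severity cannot be classified. Report the AE-only rate and the moderate/severe rate beside it, so that comparison with published rates remains possible.
2. Make the forms agree, in one of two ways:
   - add Mild and cannot-be-classified boxes to the AE form and change the entry rule in Appendix XVIII; or
   - amend the documentation section and the notes in Appendices IX and XII so that the device events form is the single source for these events. That form then needs a cannot-be-classified option and a field marking each entry as AE, malfunction or expected side effect.
3. Optional wording: in the sample-size section, say which definition the 2% uses and call the calculation one of precision. The figure 335 stays.

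The cost is a few sentences and two form pages, with no extra clients or visits. If enrolment has begun, device events forms already filed must be re-read to class each entry. The reported rate may be slightly higher than under the three-grade rule.

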 - A description of each adverse event by type, severity, time of detection (days post-application and/or post-removal) captured as date AE is diagnosed, clinical management, and resolution. The likelihood of relatedness to having undergone VMMC and relatedness specifically to the ShangRing device will be determined. AEs will be defined using the definitions in the second edition of the VMMC Adverse Event Action Guide.²⁴ These are specific to each AE type, but in general:
 - Mild: classification indicates minimal or no intervention is required beyond reassurance and observation;
 - Moderate: classification relates to those AEs that are neither mild nor severe, require intervention, and are usually managed on-site;
 - Severe: classification requires extensive intervention with referral or specialist input.
 - Note: a Serious Adverse Event (SAE) is a standard definition used across many types of interventions. In the context of VMMC, all AEs that meet criteria for severe should also be classified as SAEs. In addition, SAEs also include any event that:
 - Results in death

- Is life threatening
- Requires intervention to prevent permanent disability or incapacitation (including deformity), or results in permanent disability or incapacitation (including deformity)
- Requires hospitalization or referral to a specialist for higher level care or intervention.
- (Note: device displacement is included as an AE both in the moderate and severe classifications – see Appendix XV).

Secondary Endpoints

- Determine the training needed for proficiency, including number of procedures required under supervision to become certified as fully proficient. This will involve analyzing AE rates stratified by during training and post-training in addition to overall.
 - Determining whether various cadres are trainable as safe providers. This would involve analyzing AE rates stratified by provider cadre.
- Document client acceptability and satisfaction, to be measured by the following:
 - Time for client to return to normal activity, including work and routine tasks.
 - Clients' opinions of convenience (having device applied, 'wearing' the device for a week, and returning for device removal), acceptability, cosmetic result, and whether they would recommend VMMC, and specifically the ShangRing VMMC option to others.

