 Difficulty urinating	Other  Specify: _____	
 Excessive skin removal		
 Other		
	Complete when resolved or at final visit	
	Outcome	End/Termination
	Resolved  Resolved with sequel 	Date:
	Persistent  Unchanged 	Time:
	Unknown 	

Visual Analog Scale (VAS):

I have checked all data introduced to this form until this point and verified that they are complete, correct and reconcilable with the original documentation.

Evaluation Coordinator's Signature: _____

Date: _____

Client ID:

Adverse Events (AE) Form

Has the participant experienced a moderate or severe AE per protocol? If "No", do not enter information on this form. If the AE is defined as severe, notify the principal investigators based on the evaluation protocol.

Adverse Event	Start/Onset	Status	Device Event Number
	Date: Time: Date/time observed (if different):	New  Ongoing 	
	Action	Severity (Consult definitions for grading classification)	AE Code (Consult definitions for codes)
	None  Pharmaceutical  Surgical  Non-surgical  Evaluation termination  Other  Specify: _____	Moderate  Severe  If severe, complete information below	
	Date of SAE report to evaluation investigators:	Was the SAE a result of protocol departure? Yes  No  If "Yes," please specify:	
	Date of last visit and last visit number:	Date the device was applied:	
	Please describe the SAE in block letters (use following page if additional space is needed):	Choose criteria for SAE:  Death  Permanent disability  Life threatening  Hospitalization or prolongation of inpatient hospitalization  Required intervention to prevent one of the above  Other: _____	
	Outcome	End/Termination	
	Resolved  Resolved with sequel  Persistent  Unchanged  Unknown 	Date: Time:	

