Excess Skin Removal	C-SD: Excess skin removal —slight tightening of the skin observed; no surgical correction needed.	C-SD: Excess skin removal —pulling of scrotal skin onto the penile shaft and wound disruption.	C-SD: Excess skin removal —wound appearance is such that the wound has gaping edges or large or deep defects such that without revision, there would be significant scar formation.
SX: Sexual Effects/Undesirable Sensory Changes	C-SX: Occasional inability to have erection or dissatisfaction with sexual performance, no psycho-behavioral consequences.	C-SX: Post-operative changes that consistently impair or preclude sexual function for 3 to 6 months after surgery not present prior to surgery.	C-SX: Post-operative changes that consistently impair or preclude sexual function for greater than 6 months after surgery that were not present prior to surgery.
WD: Wound Disruption	C-WD: Wound disruption but not extensive enough to require suturing for wound closure.	C-WD: Muco-cutaneous gap > 1.0 cm in width, but no exposure of deeper tissue	C-WD: Wound disruption exposing tissue deeper than subcutaneous tissue or requiring surgical intervention such as suturing or debridement.
OA: Other AEs, Excess swelling of penis/scrotum including hematoma; other	Excess swelling —mild swelling without signs of on-going bleeding.	
Excess swelling—symptoms/signs that require clinical intervention, but not surgical exploration.
 
Other—other adverse events related to surgery that result in disability (as evidenced by loss of work or cancellation of normal activities) lasting for at least 4 days after surgery but not more than 7 days.
	
Excess swelling—surgical exploration required to control bleeding or remove haematoma or symptoms/signs so extraordinary as to cause disability (as evidenced by loss of work or cancellation of normal activities) lasting for at least 8 days after surgery or device placement or removal as pertinent.

			Other —other AE(s) related to the surgery that result in disability (as evidenced by loss of work or cancellation of normal activities) lasting for at least 8 days after surgery or device placement or removal, or result in hospitalization or referral/transfer to another facility.

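### Expedited reporting and the AE form's serious-event block are triggered by severity alone, although the protocol defines serious AEs more widely

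*Protocol*

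**What the plan says.** **Definition.** The Primary Endpoint section first sets a minimum: "In the context of VMMC, all AEs that meet criteria for severe should also be classified as SAEs". It then widens the set: "In addition, SAEs also include any event that" meets one of several outcome criteria. These are death, threat to life, intervention to prevent lasting disability (or the disability itself), and finally "Requires hospitalization or referral to a specialist for higher level care or intervention".

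**Assessment and documentation.** Adverse Events Management asks for moderate, severe and serious AEs to be documented and reported even when they seem unrelated to the procedure. Adverse Event (AE) and Other Device-Related Incident Documentation has a physician from another site judge each AE for severity, seriousness and relatedness. It says the forms will carry seriousness, and it requires a form for severe and serious AEs and for every AE that leads to admission.

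**Expedited report.** The same section then limits the 24-hour rule to one term: all "severe AEs must be reported to the CDC" within 24 hours. A separate sentence sends notifiable AEs through PEPFAR and national channels.

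**Forms (Appendix XVIII).** The AE form, used for moderate and severe AEs, instructs: "If the AE is defined as severe, notify the principal investigators based on the evaluation protocol". Its severity cell reads "If severe, complete information below". The SAE report date, SAE description and SAE criteria follow. The device-events form has boxes for severity and for relationship to the device, but none for seriousness.

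**Analysis (Analysis Overview).** "Adverse event rates will be presented by seriousness, severity, relation to device and outcome by site and by cadre".

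**The concern.** The protocol keeps serious and severe apart when it defines, assesses, documents and tabulates AEs. It uses severe alone where it sets the 24-hour report, the notice to the principal investigators and the entry to the SAE block. If an AE can be serious without being severe, those three steps miss it.

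Two things are at stake. First, the sponsor would get no 24-hour report of a client who was admitted or referred with an AE graded moderate. Second, the analysis promises AE rates by seriousness as well as by severity. If seriousness reaches the data only through a block that opens on a severe grade, the seriousness table adds nothing to the severity table and may undercount serious AEs. Safety is the primary endpoint of this evaluation, so that table will be read closely.

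**Working it through.** No published figure has to be reproduced. The check is whether the two sets really differ and, if so, where an event in the gap ends up.

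**Step 1. Is serious wider than severe by definition?** Yes. Every severe AE is serious, and the outcome criteria add others whatever their grade.

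**Step 2. Does the grading table close the gap?** For most rows of Appendix XIX it does. In the rows for bleeding, infection, device displacement, anesthetic problems, scarring, difficulty urinating and other surgery-related AEs, the severe cell names admission, transfer or referral in some form.

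Some rows leave it open:

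- *Wound disruption.* Moderate is "Muco-cutaneous gap > 1.0 cm in width, but no exposure of deeper tissue". Severe needs deeper exposure or surgical intervention. Neither admission nor referral is named.
- *Pain coded A2/B/C.* Moderate and severe are separated by days of disability or by pain score (5–7 against 8–10). Neither admission nor referral is named.
- *Excess swelling.* Severe needs surgical exploration or at least 8 days of disability. Neither admission nor referral is named.
- *Excess skin removal and sexual effects.* Their severe cells are also silent on both.
- *Admission unrelated to the surgery.* The severe cell for other AEs names admission, but only for AEs related to the surgery. Adverse Events Management nevertheless wants unrelated serious AEs reported.

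So the set of serious but not severe AEs is not empty by construction.

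**Step 3. Follow one such event.** Take a client whose wound gap exceeds 1.0 cm without deeper exposure, who is referred to a specialist and needs no surgical intervention.

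- Grade by his row of Appendix XIX: moderate.
- Status under Primary Endpoint: serious, because of the referral.
- Device-events form: completed, with no box for seriousness.
- AE form: completed, because moderate AEs qualify. Moderate is ticked, so the instruction to complete the SAE fields does not apply.
- Notice to the principal investigators: not triggered.
- 24-hour CDC report: not triggered.

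The event is on record, but as a moderate AE.

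**Step 4. Does the form's own checklist match the definition?** Not fully. It lists death, permanent disability, threat to life, admission or prolonged admission, intervention to prevent one of these, and a free-text other. Specialist referral, which the definition names, has no box.

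**Step 5. Can the class be sized?** No. Table 1 of the protocol (field study, HIV-negative men) gives 16 moderate and 2 severe AEs. If a fraction f of the moderate AEs had been admitted or referred, the serious count would be 2 + 16f against 2 counted through severity. The protocol gives no value for f. At f = 0 the count is 2 and nothing is missed. Nor does f apply to all 16, since only the AE types in Step 2 are exposed, and wound dehiscence (n = 9) is the only type whose count is given. For scale only: at the planning rate, 575 × 0.02 = 11.5 clients with an AE are expected, so serious events would be few and one misplaced event would show. That does not say that one will occur.

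**The case against.** The other side has several sound points.

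- **The body text does require seriousness to be handled.** A reader might infer that the protocol treats the two terms as one, or that a serious AE graded moderate goes unrecorded. The documents do not support that. A physician judges seriousness for each AE, and serious AEs and admissions must have a form. The methods are placed in an SOP manual that is not shown. What remains is that the supplied form does not carry out this requirement for a moderate AE.
- **The form may be looser than it reads.** Outcome and end date also lie below the severity cell and are needed for moderate AEs, so the instruction cannot bar everything beneath it. The layout was flattened in extraction, and the contents of the follow-up log in Appendix XV are not visible. This is why the right word is that seriousness *may* not be captured. The investigator notice and the CDC rule do not depend on layout.
- **The class is narrow.** Most rows already force a severe grade on admission, transfer or referral, and the general definition of severe mentions referral or specialist input. That definition, however, asks for extensive intervention with them, and the protocol says that grading is specific to each AE type.
- **The sponsor may choose its own 24-hour trigger.** No rule in the protocol sets a clock for all SAEs, so limiting it to severe AEs breaks no stated deadline. Some of these events may also travel as notifiable AEs, but that term is not defined here and its coverage is unknown.
- **There is other oversight.** A reader might infer that expedited reports are the only safety signal during enrolment. The protocol also has daily data upload, analysis in parallel with recruitment, monthly stakeholder updates and possible sponsor monitoring.

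Finally, a reader might try to turn the 16 moderate and 2 severe AEs of Table 1 into a percentage undercount. That would need an assumed fraction admitted or referred. The documents give none, and zero cannot be excluded.

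**Conclusion.** The point holds in a limited form. The definition of serious, and the rules that require seriousness to be assessed and documented, do not match three operating triggers: the 24-hour CDC report, the notice to the principal investigators and the entry to the SAE block. An AE that is serious but not severe is possible for a few types in Appendix XIX and for admissions unrelated to the surgery. It would be recorded but not expedited. Its seriousness might not be captured, and the tabulation by seriousness could then be too low.

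The class is probably small and may be empty, so no size is claimed. The conclusion on expediting rests on the text alone. The conclusion on the table rests on two further assumptions: that staff follow the form's severity instruction as written, and that the physician's judgement of seriousness does not reach the data by another route. The correction is worth making because it is cheap and removes a contradiction in safety reporting.

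**What to change.** 1. In Adverse Event (AE) and Other Device-Related Incident Documentation, extend the 24-hour CDC report to all severe and all serious AEs, as defined under Primary Endpoint.
2. On the AE form in Appendix XVIII, change both the line that opens the SAE block and the line on notifying the principal investigators, so that each applies if the AE is severe or if any SAE criterion is met.
3. Add referral to a specialist to the form's SAE checklist, to match the definition.
4. Tabulate seriousness in the analysis from that field, not from the severity grade.
5. While editing, correct the cross-reference: the text points to Appendix XIV for the AE form, but Appendix XIV is the day-3 call form and the AE forms are in Appendix XVIII.

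The cost is one sentence in the protocol, a few lines on a form, a few more 24-hour reports and possibly a slightly higher reported SAE rate. The change affects recording and reporting only. It leaves the severity grades and clinical management as they are.
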